#### **4.6 Pre-transplant Caregiver Evaluations**

Based on prior work, our Study Team has experience obtaining Caregiver Demographics on a user-friendly electronic format via Qualtrics directly through the Roadmap 2.0 app. The following data will be collected (i.e., caregiver self-report) within 30 days of randomization, including demographic, caregiving, and personal health variables, such as marital status, alcohol/tobacco use, education, employment, annual household income, use of technology, relationship to the patient, number of household members, health insurance status, number of years and number of hours per week (of caregiving), health comorbidities. Caregivers may also be asked in the onboarding session about their own health and any medications that they may be taking.

#### **4.7 Pre-Intervention Evaluation**

PROMIS Patient-Reported Outcomes (PROs) – Well-being or HRQOL assessments will be obtained at baseline, pre-intervention. The surveys will be

obtained through Qualtrics which will be linked directly to the Roadmap 2.0 app on mobile phones. Based on prior work, our Study Team has experience administering PROMIS PROs on mobile devices.

#### **4.8 Post-Intervention Evaluation**

PROMIS Patient-Reported Outcomes (PROs) Well-being or HRQOL assessments will be obtained at days 30 (+/- 14) and 120 (+/- 30) post-HCT, during and at the end of the intervention period, respectively. The surveys will be obtained through Qualtrics, which will be linked directly to the Roadmap 2.0 app on the mobile phone. Based on prior work, our Study Team has experience administering PROMIS PROs on mobile devices. If a participant relapses, our team will continue to collect clinical data post-transplant. In the event of a relapse, the patient will be censored, and we will not collect any further surveys from the patient or caregiver.

Missing surveys will not be considered a protocol deviation.

#### **4.9 Participant Withdrawal**

At any time, a participant may request that her or his data no longer be collected, that her/his data be removed from the study database, that their physiologic data no longer be collected or used for research now or in the future. The participant may make this request to the Research Coordinator or to any member of the Study Team or the BMT clinical team. The participant's research information will be deleted from the study database (with a comment that the participant withdrew consent for collection). Upon withdrawal, the participant may keep all physiological monitoring devices used in the study. A note will be made in the study record documenting the reason the patient withdrew from the study.

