### **3.0 STUDY ENDPOINTS**

#### **3.1 Primary Endpoint**

The primary endpoint is caregiver HRQOL, as assessed by the PROMIS Global Health scale, at day 120 post-HCT. To be evaluable for caregiver HRQOL, the caregiver must complete this scale at day 120 post-HCT. Caregivers of patients who relapse or die before this endpoint will not be evaluable for this endpoint; both caregiver and patient will be censored on the date the patient was last examined. See **Appendix D** for a copy of all PROMIS PROs.

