### **5.3 Study Duration**

Participants will be followed on intervention for 120-days post-transplant for primary, secondary, and exploratory endpoints. Subjects will remain in follow-up for 1-year post-HCT. The study team will have access to the electronic medical records for 1-year post-HCT.

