## **5.7 Sample Size Considerations**

The power calculation was completed by [name] using simulations in the statistical package R. Our primary endpoint (i.e., caregiver health-related quality of life from the PROMIS® Global Health scale) is focused solely on this outcome in caregivers, while our secondary endpoints are based on outcomes for both caregivers and patients. Given this, we determined our sample size based solely on caregivers. The age- and sex-adjusted norm for the Global Health scale is 50 points, with a standard deviation of 10 points. These statistics have been shown to be generalizable to the allogeneic BMT population. Our study will have power of 0.80, assuming a two-sided Type I error rate of 0.05, to detect an effect size of 0.5 between the intervention and control arms if 67 caregivers are enrolled in each arm. A mean difference of one-half a standard deviation is biologically meaningful

and is considered a medium effect size for clinical trials. We will accrue a total of 83 caregivers in each arm to account for dropout, assuming a 5% failure to undergo BMT, 8% death before day 120, and 10% missing day 120 PRO from participants. These percentages are inflated but based on adjustments of published BMT data.

Because our main goal is to assess the primary objective in adult allo dyads, we plan accrue approximately 260 dyads with adult patients, as that is the expected number of total adult dyads needed to enroll at least 166 allo dyads. We also plan to enroll approximately 40 dyads with pediatric patients in the time it takes to enroll the 260 adult dyads.

PROMIS® measures use Item Response Theory (IRT), a family of statistical models that link individual questions to a presumed underlying trait or concept of global health represented by all items in the scale. PROMIS® instruments are scored using item-level calibrations. The most accurate way to score a PROMIS® instrument is to use the HealthMeasures Scoring Service, which our Study Team has experience with ([name], Co-I and [name], Co-I). This method of scoring uses “response pattern scoring,” which uses responses to each item for each participant. Response pattern scoring is especially useful when there is missing data (i.e., a respondent skipped an item), or different groups of participants responded to different items).

There are four key features of the score for PROMIS® Global Health:

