## **5.10 Analysis Populations and General Analysis Guidelines**

### **5.10.1 Primary Analysis Population**

All participants enrolled, consented, and completing at least the baseline outcome measures will be included in the primary analysis population. Analyses for the primary and secondary endpoints will use the primary analysis population: Caregivers of adult patients [age  $\geq 18$  years] will be analyzed separately from caregivers of pediatric patients [age 5-17 years]). The primary analysis will occur once all patients have been followed for 120-days post-transplant, data adjudication completed, and data are locked.

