## **5.11 Analysis of Primary Endpoint**

Analysis will be an intent-to-treat analysis that includes all caregivers. Mean Global Health scores for each arm at day 120 will be compared using a two-sample *t*-test (or Wilcoxon Rank Sum test if non-normality is apparent) with a significance level of 0.05. Linear regression models will be performed to complement the results of the *t*-test and adjust for specific baseline caregiver characteristics (e.g., demographic, social, environmental) to increase the precision of our inference. We plan to do analyses separately for allo dyads, auto dyads, and pediatric dyads, although we have only powered the study for the analysis in the allo dyads. There is a possibility that patient characteristics will be unbalanced since our randomization scheme will be applied to caregivers. Thus, our models also will assess potential moderating or mediating effects, described below.

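### As written, Section 4.9 deletes a participant's data for every kind of withdrawal request, which conflicts with Sections 5.10.1 and 5.11 and can discard day-120 scores already given

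*Combined protocol and SAP*

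**What the plan says.** Section 4.9 opens by listing separate requests: "a participant may request that her or his data no longer be collected, that her/his data be removed from the study database", and also that physiologic data be neither collected nor used from then on. The consequence that follows is not tied to any one of these. The participant's "research information will be deleted from the study database (with a comment that the participant withdrew consent for collection". A note of the reason for withdrawal is kept as well. No section says that data collected before a withdrawal are retained.

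The analysis sections assume otherwise. Section 5.10.1: "All participants enrolled, consented, and completing at least the baseline outcome measures will be included in the primary analysis population". Section 5.11: "Analysis will be an intent-to-treat analysis that includes all caregivers". Section 5.13.2 plans baseline-adjusted regressions of the day-30 and day-120 scores and a linear mixed model of all three time points.

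Two further rules set the limits of the point. Section 3.1 states: "To be evaluable for caregiver HRQOL, the caregiver must complete this scale at day 120 post-HCT". Section 5.3 states: "Subjects will remain in follow-up for 1-year post-HCT". Under Section 4.9 a request may come at any time, so it may come after the primary outcome has been recorded.

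**The concern.** A caregiver who completed baseline and later asks only that collection stop belongs to the population in Section 5.10.1, but under Section 4.9 has no data left to analyse. Both rules cannot be followed for that person.

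Ordinary dropout leaves a partial record. Deletion goes further in two ways. It can turn an observed primary outcome into a missing one. It also removes the earlier scores that show who left and that a longitudinal model would use. Withdrawal happens after randomisation, the trial is unblinded (Section 5.5), and intervention caregivers have app components A to D while controls have only D (Appendix B). Reasons for leaving could therefore differ by arm. With the data gone, that could not be examined.

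**Working it through.** **1. Which requests does deletion cover?** The requests in Section 4.9 are distinct, while the deletion sentence has no condition. The comment to be recorded refers to consent for collection, which fits a request to stop collecting at least as well as a request for removal. The literal reading is that all requests lead to deletion.

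**2. What does deletion change, by time of withdrawal?**

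| Withdrawal | Day-120 t-test (5.11) | Other planned use |
|---|---|---|
| Before day 30 | No score whether data are kept or deleted | Baseline lost |
| After the day-30 survey, before day 120 | No score whether data are kept or deleted | Baseline and day-30 lost to the regression and mixed model (5.13.2) |
| After the day-120 survey, within 1 year | Observed score lost because of deletion | All three time points lost |

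The last row is the only one in which the rule itself alters the primary comparison. That window is about 365 − 120 = 245 days per caregiver. Section 5.10.1 places the primary analysis after all patients have reached day 120, and accrual is planned over 5 years (Section 5.2). For many caregivers, much or all of this window would pass before data lock.

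**3. The plan's own figures (Section 5.7).** Inputs: "assuming a two-sided Type I error rate of 0.05", power 0.80, effect size 0.5, SD 10, hence a 5-point difference.
- A two-sample t-test needs 63.77, so 64 per arm. Dividing by the Wilcoxon efficiency of 0.955 gives 66.8, so the stated 67.
- At 67 per arm, power is 0.819 for the t-test and 0.804 for a simulated Wilcoxon test. The stated figure reproduces.
- The attrition allowances are 5%, 8% and 10%, total 23%: 67 × 1.23 = 82.4, so the stated 83. There is no separate term for withdrawal or deletion.

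**4. Power if observed day-120 scores are deleted.** With planned attrition only, 83 × 0.95 × 0.92 × 0.90 = 65.3 evaluable per arm, t-test power 0.809. Let w be the share of these caregivers whose recorded day-120 score is later deleted. The documents give no value, so w is assumed, and n = 65.3 × (1 − w).

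| Assumed w | n per arm | Power |
|---|---|---|
| 2% | 64.0 | 0.801 |
| 5% | 62.0 | 0.789 |
| 10% | 58.8 | 0.767 |
| 15% | 55.5 | 0.742 |

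Caregivers who withdraw before day 120 do not count towards w. They have no day-120 score to delete and may already be in the 10% allowance for missing day-120 outcomes.

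**The case against.** The strongest reply is that the deletion sentence only describes how a removal request is carried out. That is a possible intention, but the text does not say so, and the recorded comment leans the other way. The consent form is not among the documents reviewed and may separate the routes. If it does, Section 4.9 should match it.

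Several stronger readings are tempting, and the documents do not support them.

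- *Deletion is what makes intent-to-treat impossible.* Other rules already limit it. Section 3.1 makes caregivers of patients who relapse or die non-evaluable, Section 4.8 stops surveys after relapse, and Section 5.10.1 requires completed baseline measures. Rewriting Section 4.9 removes one obstacle, not all.
- *The rule biases the primary contrast by a calculable amount.* One could multiply an assumed difference in withdrawal fractions by an assumed score gap, for example 0.05 × 3 = 0.15 up to 0.15 × 8 = 1.2 points. That describes missing day-120 scores in general. For withdrawal before day 120 it is the same whether earlier data are kept or deleted, because the planned t-test does not use them and no imputation is planned. It does not measure the effect of Section 4.9.
- *Participant flow by arm is lost.* Section 5.4 provides three stratified randomisation lists, used in order and without reuse, and Section 4.9 keeps a withdrawal comment and reason. Counts by arm are largely recoverable, although the plan does not guarantee it.
- *Anyone who stops answering surveys is erased.* Section 4.8 does not treat a missed survey as a deviation. Deletion follows a request about data, not silent non-response.

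It is also fair to say that withdrawals after day 120 may be few, since the planned surveys are finished by then. The documents give no rate either way.

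**Conclusion.** The point holds as a conflict between sections with limited, identifiable consequences. As written, Section 4.9 cannot be followed together with Sections 5.10.1 and 5.11 for a caregiver who completes baseline and later asks only that collection stop.

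Two losses follow from the rule: day-120 scores already given by caregivers who withdraw during the follow-up year, and, for earlier withdrawals, the baseline and day-30 scores needed for Section 5.13.2 and for comparing withdrawers with completers by arm.

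The size of the first depends entirely on an unstated rate. An assumed 2% to 10% deleted lowers power from 0.81 to between 0.80 and 0.77, so at low rates the power cost is small. The second is a loss of information with no figure attached. The conclusion rests on the literal reading of Section 4.9.

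**What to change.** Rewrite Section 4.9 with two routes.

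1. **Stop further collection**, of all data or of physiologic data only. New collection ends, and data collected up to that date are kept and analysed.
2. **Removal.** Data are deleted only on an explicit request for removal, and only the data named in that request.

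In both routes keep the study ID, arm, stratum, and randomisation and withdrawal dates, so that every randomised dyad is counted.

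The cost is protocol wording, plus consent wording if the consent form repeats the current rule. The right to ask for removal is unchanged, so some data may still be lost through route 2. Deleted data cannot be recovered, so the change is worth making promptly. The relapse, death and baseline-completion rules need their own treatment if Section 5.11 is to keep its intent-to-treat description.

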#### **4.10 Study Regulations**

The trial will be performed in accordance with all applicable regulatory requirements and laws. All investigators, research administrators, and other personnel who are involved in the studies will at a minimum be required to complete an online tutorial on the protection of human research subjects (this may be site-specific or through a multi-institutional platform like CITI). All sites will send their training certificates to the University of Michigan.

All patient subjects will receive care either inpatient or outpatient through one of the participating sites by trained medical personnel skilled in the care of BMT recipients who will be responsible for ensuring necessary medical or professional intervention in the event of adverse events to subject.

#### **4.11 Risks**

- 4.11.1 Wearable Sensor Device (Fitbit): Patient Subjects who agree to wear a device (s) for data collection may experience mild skin irritation, which will be monitored by the care team. The subject can decline to wear the device(s) or request to try a different device(s) that may be more comfortable. They will be instructed to remove the device before any scans or radiation therapy.
- 4.11.2 Confidentiality: There is a possible risk of loss of confidentiality. However, every effort will be made to keep your medical information confidential. We will code data by assigning a number to each individual patient and then store the data by that number. No mention of patient subject identities is made in analyses of the data or in any publications, which result from such research.

#### **4.12 Adverse Event Reporting Requirements**

No adverse events related to this intervention are expected, as the focus of this intervention (if randomized to Roadmap 2.0) is on informational resources as well as positive activity exercises. If the PI or study team judges that an adverse event is related to the subject's participation in this clinical trial, it will be reported to IRBMED per institutional guidelines. The coordinating site will meet with other sites at least once a month to review any potential adverse events. The University of Michigan site will report any adverse events for all the performance sites.

Participants will be considered on study for approximately 120-days post-HCT and are likely to have adverse events completely unrelated to the intervention but related to their underlying disease and/or allogeneic/autologous HCT. One example of a study-related adverse event that would be reported could include loss of confidentiality of data. Examples of events that would not be reported would include any complications from any procedures (specifically, transplant-related), surgeries, treatments (e.g., GVHD, chemotherapy, radiation therapy), or death unless due to the study.

#### **4.13 Participant Data Security and Compliance**

The wearable sensor device monitoring system data will be downloaded to a secure, password-protected University of Michigan core imaged computer and stored with subject codes in [name] [name]'s Laboratory (MPB) following rules for secure data storage (e.g., M+Box, Dropbox, RedCAP). Research devices will not interface with MiChart. All study personnel will complete training related to Human Subjects Research Protections and HIPAA. All study information will be stored in a password-protected encrypted files and identified by case number. The technologies proposed in this proposal have all been carefully reviewed and approved by the governing bodies at Michigan Medicine. All regulatory and security requirements have been met and have been fully documented in accordance with the policies and best practices that govern the use of technology

for patient care and research at Michigan Medicine. The MiChart web services were built and are supported by HITS, and their use for this project has been approved by HITS. All standard procedures and protocols for security and data integrity that apply to this project are being followed. All PHI will be stored in the HITS Oracle Database. Each study participant's contact information will be securely stored in RedCap for use during the study. Each site will keep a master list of their site's participant names and matching participant IDs. The coordinating center will have access to this information, though participating sites will not see subjects enrolled at other sites. Site personnel will keep subject information in password-protected files on a secure server or in a secure environment (e.g., locked cabinet, restricted access). No one other than the study team at the study site will have access to their site's master list (except when needed for study monitoring). At the end of the study, all records will continue to be kept in a secure location for as long a period as dictated by the reviewing IRB, Institutional policies, or funding agency requirements.

Study participant research data, which is for purposes of statistical analysis and scientific reporting, will be transmitted to and managed by the University of Michigan. Individual participants and their research data will be identified by a unique study identification number, where possible. The study data entry and study management systems (e.g., Roadmap app, REDCap, Qualtrics, M-Box, Dropbox, Fitbit®, etc.) used by clinical sites and by University of Michigan research staff are secured and password protected. Data will also be entered into Oncore/Velos as requested by the Rogel Cancer Center. At the end of the study, all study databases will be coded using subject IDs and archived at the University of Michigan.

#### **4.14 Data and Safety Monitoring Plan**

This study will be monitored in accordance with the NCI approved University of Michigan Rogel Cancer Center Data and Safety Monitoring Plan, with oversight by the Rogel Cancer Center Data and Safety Monitoring Committee (DSMC).

The Study Principal Investigator will provide ongoing monitoring of data and patient safety in this trial and conduct regular data review with participating sites.

The Study Principal Investigator and/or the Study Coordinator/Delegate will review data and patient safety issues with participating sites per a defined bi-annual meeting cadence. Depending on the protocol activity, the meeting cadence may be more frequent. This data review meeting may be achieved via a teleconference or another similar mechanism to discuss matters related to:

- Enrollment rate relative to expectations, characteristics of participants
- Safety of study participants (SAE reporting, unanticipated problems)
- Adherence to protocol (protocol deviations)
- Completeness, validity and integrity of study data

- Retention of study participants

The Study Coordinator/Delegate is responsible for collating the data from all participating sites and completing the Protocol Specific Data and Safety Monitoring Report (DSMR) form to document the data review meeting discussion.

The DSMR will be signed by the Study Principal Investigator or designated Co-Investigator and submitted to the DSMC on a bi-annual basis for independent review.

#### **4.15 Quality Assurance and Audits**

The Data and Safety Monitoring Committee can request a 'for cause' quality assurance audit of the trial if the committee identifies a need for a more rigorous evaluation of study-related issues.

A regulatory authority (e.g. FDA) may also wish to conduct an inspection of the study, during its conduct or even after its completion. If an inspection has been requested by a regulatory authority, the site investigator must immediately inform University of Michigan Rogel Cancer Center that such a request has been made. Audits will be performed by the University of Michigan Rogel Cancer Quality Assurance Review Core (QARC), per institutional guidelines.

During an audit access to relevant documentation, including patient records, must be given by the site investigator to the University of Michigan Rogel Cancer Center representative conducting the audit to verify consistency of data collected with the original source data.

The University of Michigan Rogel Cancer Center expects the relevant investigational staff to be available to facilitate the conduct of the visit, that source documents are available at the time of the visit, and that a suitable environment will be provided for review of study-related documents. Issues identified during these visits will be communicated to the site and are expected to be resolved by the site in a timely manner.

